5.3 Study Follow-up

After study RBUS is obtained, patients will be followed prospectively by telephone call at 2 weeks, 4 weeks and 42 days (6 weeks) from the time of diagnostic CT. They will be followed for spontaneous stone passage, and be asked to keep record of when this occurs. During the 42-day follow up, their course will also be monitored for ED visits, surgical intervention and hospital admissions. All currently available medical records such as Clindesk, Allscripts, Compass, HMED will be reviewed retrospectively to follow participants' clinical course, specifically to determine the need for surgical intervention or spontaneous stone passage. Billing records may also be used to identify patients who underwent surgical intervention based on CPT codes. Evaluation of the patient's emergency room records with a focus on their presenting symptomatology and initial evaluation by the emergency provider will be performed. Any additional laboratory tests and/or imaging obtained during their emergency room or office visit will also be reviewed and collected for study purposes.

Surgical intervention, including ureteral stent or nephrostomy tube placement, ureteroscopy/laser lithotripsy, or extracorporeal shockwave lithotripsy (ESWL) will be instituted, as per standard of care. A follow up telephone call at 2 weeks, 4 weeks and 42

days (6 weeks) from the time of diagnostic CT will be performed in case of care received outside of the Barnes-Jewish Hospital (BJH) system and medical records reviewed for ER visits, hospital admissions and surgical intervention.

5.4 Risks and benefits associated with study participation

The results from this study will not directly benefit the patients who agree to participate, however, we hope they will help define the role of RBUS with UJA as an alternative to ionizing radiation-based studies. Knowledge gained from this study may help us improve our stone management practice.

Participation in this study will not affect the patient's risks associated with the standard of care stone management. There are no risks associated with an abdominal ultrasound. Patient may feel slight discomfort if he or she is experiencing abdominal pain.

Risks associated with the medical expulsive therapy and/or surgical procedure for stone management will be discussed with all participants as part of their clinical care and clinical consent for the procedure will be obtained.

5.5 Duration of Follow-Up

Patients will be followed by telephone call at 2 and 4 weeks and 42 days (6 weeks) after diagnostic CT. They will have a clinic visit with their urologist per standard of care practice.

5.6 Criteria for Removal from Study

If at any time the constraints of this protocol are considered to be detrimental to the patient's health and/or the patient no longer wishes to continue with study participation, the patient should be removed from the study and the reason(s) for discontinuation documented.

Otherwise, the patient will be followed and evaluated as described.

6.0 DATA AND SAFETY MONITORING

Participation in the proposed study will not pose any risks to the participants beyond what is expected from the standard of care stone management.

The PI will monitor the study for any reportable events from the time of the study RBUS to day 42 post diagnostic CT. All HRPO guidelines for reporting events meeting defined criteria will be followed.

7.0 STATISTICAL CONSIDERATIONS

7.1 Study Objectives and Endpoints

Primary Outcome:

To determine if RBUS with UJA is prognostic of stone passage versus need for

surgical intervention:

1. Passage of stone as assessed by patient self-report and/or collection of stone or imaging.
2. Need for further medical attention as collected by chart review and phone interview for ED visit, hospitalization, or need for surgical intervention during the 42-day follow-up period.

Secondary Outcomes:

1. To determine if RBUS with UJA, in conjunction with standard of care laboratory data and history and physical confers non-inferior information compared to non-contrasted CT:
 - a. Urologist will review the patient's de-identified/coded history and physical, laboratory studies, and RBUS with UJA and make an assessment and treatment recommendations. The urologist will be blinded to the results of the CT. Comparison will be made between the CT diagnosis and the blinded assessment of the urologist.
2. To determine if the natural history and rate and time of stone passage for ureteral stones of differing locations (proximal, mid or distal ureter) and sizes (<2mm, 2-4mm, 5mm, 6-7mm, 9-10mm):
 - a. Assessment of the stone location and size to be conducted by a radiologist.

7.2 Study Design

This is a single institution, prospective study to evaluate the prognostic significance of RBUS with UJA, and its utility in providing non-inferior information compared to non-contrasted CT, as well as to evaluate the spontaneous stone passage rate of ureteral stones. The study will be conducted at Washington University and will enroll approximately 100 participants over two years.

7.3 Data Analysis

Primary objective:

This patient cohort will be analyzed retrospectively to determine whether US with UJA is predictive of spontaneous stone passage versus need for surgical intervention. Kaplan-Meier curve will be used to test time to spontaneous stone passage between the two groups. A chi-square test of independence will be used to test intervention rates between the two groups. A multivariate analysis will also be conducted controlling for such variables as age, gender, BMI, side, size of stone, and stone passage. A Cox-proportional hazards model will be used for time to spontaneous stone passage and logistic regression will be used for intervention.

Due to the unforeseen difficulty of recruitment and the uncertain assumptions of the initial power analysis, an interim statistical analysis is recommended to be performed when the recruitment reaches 50 patients. Based on the results, a decision will be made whether to continue recruitment to the initial 100 targeted patients, adjust the number of targeted patients based on a new power analysis, or to discontinue recruitment. The interim results

should not affect primary independent variables in the study as the radiologist performing the ultrasounds will not have access to the results.

Secondary objective 1:

Statistical analysis will be performed to determine diagnostic and treatment concordance between the two methods. A multivariate logistic regression model will also test patient factors that are associated with discordant results.

Secondary objective 2:

In a prospective manner, they will be followed to determine the natural history of ureteral stones with regard to stone passage. Average time to stone passage for each size category and stone location will be determined. Cox-proportional hazard models will be used to determine significant factors affecting time to stone passage.

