1.2 Rationale

Due to the increasing use of CT and concern for radiation exposure, it is important to consider alternative diagnostic imaging modalities. We seek to evaluate patients who present to the Barnes-Jewish Hospital (BJH) ED and to the Urology office with renal colic who have been diagnosed with a ureteral stone. We seek to determine whether the findings on ureteral jet assessment (UJA) by RBUS are predictive of a patient's clinical outcome. Specifically, we seek to

evaluate whether the presence, absence or relative strength of the ipsilateral ureteral jet can predict spontaneous passage versus need for surgical intervention over a 42-day (6-week) time period. As many patients have a life-long affliction with nephrolithiasis[1], the potential for a considerable aggregate accumulation of radiation exposure over their lifespan can be excessive and should not be overlooked [5, 7, 8]. This patient population, especially those first diagnosed at a young age, would benefit from imaging modalities that do not involve radiation.

Evaluating the significance of UJA and RBUS in patients with renal colic will help define the role of this imaging modality, as an alternative to ionizing radiation-based studies. The prognosis of urolithiasis based on UJA will be defined, as well as the natural history of stones managed expectantly. We hypothesize that UJA showing weak or absent ureteral jet will predict obstruction and a higher rate of surgical treatment compared to spontaneous passage. We hypothesize that larger stones will be less likely to pass without surgical intervention.

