2.2 Secondary Objectives

1. To determine whether RBUS with UJA, in conjunction with standard of care history, physical examination and laboratory studies confers the same diagnostic information as the gold standard, non-contrast CT.
2. To determine the natural history and rate and time of stone passage for ureteral stones of differing locations (proximal, mid or distal ureter) and sizes (<2mm, 2-4mm, 5mm, 6-7mm, 9-10mm).

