5.2 Study Plan and Procedures

Study RBUS with UJA will be obtained within 10 days following CT diagnosis of ureteral calculus. Ureteral jet data will be documented and patients will be followed prospectively for 42 days at 2 weeks, 4 weeks and 42 days (6 weeks) after diagnostic CT. Specifically, patients will be followed for spontaneous stone passage and will be expected to record date of stone retrieval. If specific date of stone passage is not known, date of standard of care imaging confirming absence of stone(s) will be used as the date of stone passage. If spontaneous stone passage is not achieved, patients will be counseled regarding further standard of care treatment options including surgical stone removal. If surgical intervention is indicated, time to surgical procedure will also be recorded. This patient cohort will be analyzed retrospectively to determine whether RBUS with UJA is predictive of spontaneous stone passage versus need for surgical intervention over a 42-day period.

Interpretation of RBUS and UJA:

Abdominal radiologists will interpret the RBUS research reads. All grey scale and color Doppler examinations will be performed by means of a commercially available unit with a 1-5 MHz phased array transducer or a 1-6 curved transducer. Flow toward the transducer is assigned a red color on Doppler. For grey scale evaluation, the presence or absence of urinary tract stones, size (longest axis in mm) and location- R, L, upper pole, interpolar and lower pole of the kidneys, proximal ureter, distal ureter and bladder- will be documented. The level of the renal pelvis represents the interpolar kidney with upper and lower pole above and below this level. For this study, a urinary tract stone will be termed an echogenic focus that demonstrates either posterior acoustic shadowing and or twinkle artifact on color Doppler images. In addition, presence of hydronephrosis (mild, moderate, and severe) will be documented. For the purpose of this read, hydronephrosis will be defined as such: mild hydronephrosis - urine fills the intra and extra renal pelvis and the major calyces are dilated; moderate hydronephrosis – above + dilatation of the minor calyx with preservation of the renal parenchyma; severe hydronephrosis – above +

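### Section 7.3 gives no rule for surgery before stone passage; if surgery is censored, one minus Kaplan-Meier overstates the proportion who pass, and a plain average passage time can mislead

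*Combined protocol and SAP*

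**What the plan says.** For the primary objective, section 7.3 states: "Kaplan-Meier curve will be used to test time to spontaneous stone passage between the two groups". It then states: "A chi-square test of independence will be used to test intervention rates between the two groups". The adjusted models are Cox for time to passage and logistic regression for intervention. For secondary objective 2, the same section promises an average passage time for each size category and location, alongside Cox models.

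Surgery is central to the question. Section 2.1 sets passage against surgery over 42 days, and section 1.2 says: "We hypothesize that UJA showing weak or absent ureteral jet will predict obstruction and a higher rate of surgical treatment compared to spontaneous passage". Section 5.2 says: "If spontaneous stone passage is not achieved, patients will be counseled regarding further standard of care treatment options including surgical stone removal". It also says: "If surgical intervention is indicated, time to surgical procedure will also be recorded". Section 5.3 defines the intervention broadly: "Surgical intervention, including ureteral stent or nephrostomy tube placement", together with ureteroscopy and shockwave lithotripsy.

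The target quantity can be read in two ways. Section 1.2 speaks of defining prognosis "as well as the natural history of stones managed expectantly", which could mean passage had nobody been operated on. Section 2.2 wants "To determine the natural history and rate and time of stone passage for ureteral stones of differing locations", and section 7.2 also asks for a passage rate; both can be read as the proportion who actually pass. Section 7.1 lists stone passage as item 1 of the primary outcome.

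Sections 5.2, 5.3, 7.1 and 7.3 do not say whether a patient operated on before passage is censored at surgery, kept at risk to day 42, or counted as having a competing event.

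**The concern.** Once a stone is removed surgically it can no longer pass spontaneously. Kaplan-Meier with surgery censored treats that patient as if passage could still occur later, at the rate seen in patients not yet operated on. The curve therefore rises above the proportion of enrolled patients who pass. Because surgery is expected to differ by jet group, the distortion can differ by group too, and a passage figure read from the curve can hide or exaggerate the contrast that the trial exists to measure.

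The chi-square test does not fill the gap. It concerns intervention, and a stone still in place at day 42 has neither passed nor been operated on, so the intervention rate is not the complement of the passage rate. An average passage time has a related weakness: where surgery takes stones out early, only quick passages are left to average.

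**Working it through.** **Inputs.** From the documents: 42 days of follow-up (section 2.1) and about 100 patients (section 7.2). Not in the documents: passage rates, surgery rates, the split between jet groups, alpha, and the initial power analysis, which section 7.3 mentions but does not show. There is therefore no figure in the plan to reproduce, and every rate below is assumed. I compare normal jets with weak or absent jets as two groups, at a two-sided 5% level.

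**Step 1: a count with no hazard model.** Take 50 patients. Passages: 10 on day 7, then 5 each on days 14, 28 and 40. Surgery: 10 on day 10 and 5 on day 20. Ten stones are retained. With surgery censored, the numbers at risk at the four passage days are 50, 30, 20 and 15, so KM = (40/50)(25/30)(15/20)(10/15) = 0.333 and 1-KM = 66.7%. The proportion who passed is 25/50 = 50%.

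**Step 2: two groups.** Let p and s be the proportions passed and operated on by day 42, with constant, independent hazards. The total cumulative hazard is H = -ln(1-p-s), the passage part is Hp = H·p/(p+s), and 1-KM = 1-exp(-Hp).

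| Passed/surgery, % | H | Hp | 1-KM | Actually passed | Excess, points |
|---|---|---|---|---|---|
| 60/10 | 1.204 | 1.032 | 64% | 60% | 4 |
| 40/50 | 2.303 | 1.023 | 64% | 40% | 24 |
| 80/15 | 2.996 | 2.523 | 92% | 80% | 12 |
| 30/30 | 0.916 | 0.458 | 37% | 30% | 7 |

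The first pair hides a 20-point difference in passage. The second turns 50 points into 55, and its larger excess is in the group with *less* surgery. At a fixed passage hazard the excess grows with the surgery hazard; across groups it depends on both.

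**Step 3: the other coding.** If surgical patients are kept at risk to day 42 as not having passed, the curve at day 42 equals the proportion passed, provided there is no other censoring.

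**Step 4: can 1-KM stand for passage without surgery?** Only if surgery is unrelated to the chance of passing. Section 5.2 raises surgery when passage has not occurred, which makes that doubtful. Suppose half the stones are easy (42-day cumulative hazards 2.0 for passage, 0.2 for surgery) and half hard (0.3 and 1.5):
- passage with no surgery: ½(1-e^-2.0) + ½(1-e^-0.3) = 56.2%
- actually passed: ½(2.0/2.2)(1-e^-2.2) + ½(0.3/1.8)(1-e^-1.8) = 47.4%
- 1-KM, from the pooled passage hazard among patients still at risk: 65.5%

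Here 1-KM estimates neither quantity.

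**Step 5: average time among stones that passed.** With λ = H/42 and q = p+s, the mean is 1/λ - 42(1-q)/q.
- 60/10: 42/1.204 - 42(0.30/0.70) = 34.9 - 18.0 = 16.9 days
- 40/50: 42/2.303 - 42(0.10/0.90) = 18.2 - 4.7 = 13.6 days
- 70/15 and 45/40: both have q = 0.85, so both give 14.7 days, although 70% and 45% pass

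**The case against.** Section 7.3 uses Kaplan-Meier as a comparison of times and does not promise 1-KM as the passage rate; a rate could be reported as simple counts. That is fair. The harm arises only if surgery is censored and the curve is then read as a proportion. Censoring is the usual default, however, and the section offers nothing to prevent that reading.

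Several stronger readings are tempting, and the documents do not support them.

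- **That the planned tests are invalid.** They are not. With surgery censored, the log-rank test and Cox compare the cause-specific passage hazard correctly.
- **That passage by day 42 is never compared.** If surgical patients stay at risk to day 42, which the silent text also allows, the Kaplan-Meier comparison addresses cumulative passage. What can be said is that the only proportion explicitly tested is intervention.
- **That the average is stated to cover passers only.** It is not. This is the natural reading, since the time is undefined for other patients and no restricted mean or median is named, but it is an inference.
- **That the same data could show more passage with weak or absent jets.** In the 60/10 versus 40/50 example that needs surgical patients to be dropped (60/90 = 67% versus 40/50 = 80%), and nothing in the documents suggests dropping them.
- **That power is, or is not, safe.** Neither holds in general. At 70/15 versus 45/40, the chi-square on surgery has 82% power at 50/50, 73% with 30 normal and 70 weak or absent, and 53% at 25/25. The last case matters because section 7.3 allows recruitment to stop after the interim analysis at 50 patients.

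Section 5.3 already classes stent and nephrostomy as surgical intervention, so under a first-event rule those patients are classified. That rule only needs to be written down.

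**Conclusion.** The point holds as a gap in definition and reporting that should be fixed. Section 7.3 lacks a rule for surgery before passage and does not say which passage quantity is wanted. If surgery is censored, 1-KM overstates the proportion who pass, by 4 to 24 points in the examples, and the difference between groups can be hidden (64% versus 64% against 60% versus 40%) or enlarged (92% versus 37% against 80% versus 30%). The average passage time, on its natural reading, can favour the category in which fewer stones pass.

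The sizes rest on assumed rates and constant hazards, and step 4 on an assumed mix of stones. That 1-KM exceeds the observed proportion when surgery is censored and stones pass afterwards does not depend on those choices, as the count in step 1 shows.

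**What to change.** In section 7.3:

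1. Report passage by jet group as cumulative incidence with surgery as the competing event. Censor retained stones at day 42, and patients lost or withdrawn earlier at last contact.
2. Keep the Kaplan-Meier-based test and Cox, labelled cause-specific for passage. Report 1-KM only if labelled as passage had nobody been operated on, with its independence assumption stated.
3. Tabulate passed, surgery, retained and unknown at day 42 by jet group, and compare the proportion passed as a supportive analysis.
4. For analysis, count stent or nephrostomy as surgery, consistent with section 5.3, so that the first event decides.
5. For secondary objective 2, replace the average time with cumulative incidence of passage at days 14, 28 and 42 with confidence intervals, by size and by location.

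The cost is wording and programming. Dates of passage and surgery are already to be recorded, although section 5.2 substitutes an imaging date where the passage date is unknown, so some times will be approximate. The rule is best fixed before the interim analysis, so that the choice cannot follow the data.

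Reported passage rates will read lower than 1-KM. Intervals by size will be wide: with 20 patients per category (100 spread evenly over five sizes, assumed), 10 of 20 passing gives a Wilson 95% interval of 30% to 70%. The added test of proportion passed has modest power at 50/50: 54% for 60% versus 40%, and 74% for 70% versus 45%. It therefore supplements the planned tests and does not replace them.

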2.0 OBJECTIVES

2.1 Primary Objective

1. To determine whether use of renal bladder ultrasound (RBUS) with UJA is predictive of spontaneous stone passage versus need for surgical intervention over a 42-day time frame.

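### The primary aim is prediction, but the primary analysis plans only tests of association, with no measure of discrimination or of added value over CT stone size and location

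*Combined protocol and SAP*

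**What the plan says.** Section 2.1 sets the primary objective as whether ultrasound with UJA "is predictive of spontaneous stone passage versus need for surgical intervention over a 42-day time frame". Section 7.1 puts the same aim as prognosis: "To determine if RBUS with UJA is prognostic of stone passage versus need for" surgery. Section 1.2 states the ambition: "The prognosis of urolithiasis based on UJA will be defined", and the work "will help define the role of this imaging modality, as an alternative to ionizing radiation-based studies".

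The primary analysis in section 7.3 has three parts:

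- Time to passage, unadjusted: "Kaplan-Meier curve will be used to test time to spontaneous stone passage between the two groups".
- Intervention, unadjusted: "A chi-square test of independence will be used to test intervention rates between the two groups".
- Adjusted: a Cox model for time to passage and a logistic model for intervention. The open-ended covariate list names age, gender, BMI, side, stone size and stone passage. It does not name stone location.

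The documents nowhere mention sensitivity, specificity, an ROC area or c-index, calibration, a comparison of models with and without UJA, or a level of performance at which UJA would count as predictive. Section 7.3 states no significance level either. The concordance analysis under secondary objective 1 compares a blinded ultrasound-based assessment with CT; it does not measure prediction of the day-42 outcome.

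**The concern.** A chi-square test or a hazard ratio shows that groups differ on average. Prediction is a question about individuals: how many of those who go on to intervention had a weak or absent jet, how many of the rest did not, and how much the jet finding adds to what CT already showed. Every participant has a diagnostic CT (section 3.1), and its stone size and location are recorded at enrolment (section 5.2), so added value can be assessed for the whole cohort.

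At stake is the headline conclusion. With about 100 patients, a difference can be statistically detectable while the jet finding sorts patients only modestly better than chance. If the report rests on the planned tests, a reader will not see that, and the role of UJA in choosing between waiting and surgery could be overstated.

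**Working it through.** **Inputs from the documents.** About 100 participants (section 7.2); interim analysis at 50 (section 7.3); follow-up of 42 days (section 5.2). Significance level, power, effect size, intervention rate and the distribution of jet groups are not given, so the enrolment target cannot be reproduced. Everything below is illustration on assumed values.

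**Worked example.** Assume an equal split, 20/50 interventions with weak or absent jets and 10/50 with normal jets, and a two-sided 0.05 level.

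- Chi-square = 100 × (20×40 − 30×10)² / (50×50×30×70) = 4.76, p = 0.029. With continuity correction, 100 × (500 − 50)² / 5,250,000 = 3.86, p = 0.0495.
- Sensitivity = 20/30 = 67% (Wilson 95% CI 49 to 81).
- Specificity = 40/70 = 57% (45 to 68).
- Positive predictive value = 20/50 = 40% (28 to 54); negative predictive value = 40/50 = 80% (67 to 89).
- AUC for a single cut = (0.667 + 0.571)/2 = 0.62. Its SE = ½ × √(0.667×0.333/30 + 0.571×0.429/70) = 0.052, so the 95% CI is 0.619 ± 1.96 × 0.052 = 0.52 to 0.72.
- Correctly classified = (20 + 40)/100 = 60%. Predicting no intervention for everyone would be right in 70%.

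**Other tables at N=100 near the boundary**, by the same formulas:

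| Interventions, weak/absent v normal | p (corrected p) | Sensitivity | Specificity | AUC (95% CI) |
|---|---|---|---|---|
| 17/50 v 8/50 | 0.038 (0.065) | 68% | 56% | 0.62 (0.51 to 0.73) |
| 12/30 v 13/70 | 0.023 (0.044) | 48% | 76% | 0.62 (0.51 to 0.73) |
| 10/15 v 30/85 | 0.022 (0.045) | 25% | 92% | 0.58 (0.51 to 0.66) |

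For nine combinations (weak/absent share 15, 30 or 50%; intervention rate 15, 25 or 40%), the table that just reaches uncorrected p<0.05 at N=100 has an AUC of 0.58 to 0.64. At the 50-patient look the range is 0.62 to 0.72.

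**A larger effect.** 30/50 v 10/50 gives sensitivity 30/40 = 75%, specificity 40/60 = 67%, AUC = (0.750 + 0.667)/2 = 0.71, SE = ½ × √(0.75×0.25/40 + 0.667×0.333/60) = 0.046, and 95% CI 0.62 to 0.80. Weak discrimination is therefore a feature of results near the boundary, not of every significant result.

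**Undefined cut.** All these figures treat weak or absent jets as one positive category. Section 5.2 defines three jet groups; section 7.3 compares two and does not say which are merged.

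**The case against.** The strongest reply is that the plan already comes close. The intervention rate in the weak/absent group is the positive predictive value, and one minus the rate in the other group is the negative predictive value. Sensitivity and specificity follow from the same 2×2 table. The Kaplan-Meier curves show the chance of passage over time by jet group. The adjusted models include stone size, and testing the UJA term in such a model is, in large samples, equivalent to a likelihood-ratio test over size. The stated hypothesis is itself a group difference: "We hypothesize that UJA showing weak or absent ureteral jet will predict obstruction and a higher rate of surgical treatment". All of this stands. A reader might infer that the planned analyses say nothing about prediction or about value beyond CT findings; the documents do not support that.

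A reader might also infer that p<0.05 is the plan's rule for calling UJA predictive. No such rule is stated, and no other criterion is either.

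Two further points stand in part. First, CT size and location are only one possible benchmark: section 1.2 looks for an alternative to radiation-based imaging, and in that setting CT size might not be available. The added-value model should therefore be supportive, not a condition for success. Second, location could enter under the open-ended covariate list, but it is not named. That list does include stone passage, an outcome unknown at the time of ultrasound, so the logistic model as written could not serve as a prediction model.

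What survives is that no discrimination measure, accuracy interval, added-value measure or jet cut is prespecified. Choosing these after seeing the data invites optimism.

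**Conclusion.** The point holds as a gap between the primary objective and the planned reporting. The tests are valid for association and for the hypothesis in section 1.2, but they stop short of measuring prediction.

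On the assumed rates and splits, a result that just reaches significance at about 100 patients goes with an AUC near 0.6, with a lower limit just above 0.5 in the tables shown. It would be too strong to say that any significant result could be near-useless: a boundary result still implies some discrimination, and a larger effect implies more. The figures depend on an intervention rate and group split that the documents do not give, and on merging weak and absent jets. This is a worthwhile improvement to section 7.3, not a flaw that invalidates the study.

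**What to change.** In section 7.3:

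1. Reconcile the three jet groups of section 5.2 with the two groups being compared, and prespecify the cut. Accuracy measures are undefined until this is done.
2. Alongside the planned tests, report sensitivity, specificity, positive and negative predictive values, and AUC (or a c-index) for the day-42 outcome, each with a 95% CI. For a single binary cut, use an interval suited to a binary marker, as in the working.
3. Add one small prespecified model with CT stone size and location, fitted with and without UJA. Report the likelihood-ratio test and the optimism-corrected change in AUC as supportive results.
4. State that the conclusion about prediction will rest on these estimates and their intervals, not on a significance test alone.

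The cost is a little extra analysis on data already collected, with no new patients, visits or tests. Intervals will be wide: with an assumed 25 interventions, an observed sensitivity of 20/25 has a Wilson 95% CI of 61 to 91%, and the change in AUC will be imprecise. The conclusion may also be less favourable than a p-value would suggest.
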